6.2.2. Conventions

Unless otherwise specified, the following conventions will be applied to all analyses:

- 1 year = 365.25 days. Number of years is calculated as (days/365.25) rounded up to 1 significant digit.
- 1 month = 30.4375 days. Number of months is calculated as (days/30.4375) rounded up to 1 significant digit.
- Age will be calculated as the integer part of (date of informed consent date of birth + 1)/365.25.
- P-values will be rounded to 4 decimal places. P-values that round to 0.0000 will be presented as '< 0.0001' and p-values that round to 1.000 will be presented as '> 0.9999'.
- For laboratory results collected as ≥ x, the value of the laboratory results will be set as x. For laboratory results collected as < x, the value of the laboratory results will be set as x divided by 2.
- For by-visit observed data analyses, percentages will be calculated based on the number of subjects with non-missing data as the denominator, unless otherwise specified.
- Unscheduled measurements and retested measurements will not be included in byvisit table summaries and graphs but will contribute to the best/worst case value

where required (e.g., shift table). Listings will include scheduled, unscheduled and retest data.

- For continuous endpoints, summary statistics will include n, mean, standard deviation, median, Q1, Q3 and range (minimum and maximum).
- For discrete endpoints, summary statistics will include frequencies and percentages.

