10.3.3. Laboratory Analyses

Clinical laboratory (clinical chemistry, hematology, coagulation, and urinalysis) values will be evaluated for each laboratory parameter as appropriate. Abnormal laboratory values will be flagged and identified as those outside (above or below) the normal range. Laboratory parameters and their changes from baseline will be summarized by visit and dose level. Change from baseline will only be summarized for subjects with both baseline and postbaseline measurements.

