APPENDIX 4. CLINICAL LABORATORY ASSESSMENTS

Clinical chemistry	Hematology	Coagulation	Urinalysis ^a
Alkaline phosphatase Alanine aminotransferase Aspartate aminotransferase Albumin Total bilirubin Direct bilirubin Blood urea nitrogen or urea Potassium Sodium Total calcium Creatinine Glucose Lactate dehydrogenase Total protein Magnesium Lipase Amylase	Red blood cell count Hematocrit Hemoglobin Platelet count White blood cell count with differential (both absolute count and percentage) 
 • Lymphocyte count • Neutrophils • Monocytes • Eosinophils • Basophils 	Prothrombin time Partial thromboplastin time or activated partial thromboplastin time International normalized ratio	Specific gravity pH Glucose Protein Blood Ketones Bilirubin Urobilinogen Nitrite Leukocyte esterase
Other Screening Tests			

 • Follicle-stimulating hormone and estradiol (as needed for female subjects who are < 55 years of age with no spontaneous menses for ≥ 12 months to identify the status of no childbearing potential) • Urine (drugs screen [to include at minimum: amphetamines, barbiturates, benzodiazepines, cocaine, opiates, methamphetamines, methadone, methyl enedioxy methamphetamine, phencyclidine, and tetrahydrocannabinol]) • Breath test (alcohol screen) • Highly sensitive (serum/urine) human chorionic gonadotropin pregnancy test (as needed in female subjects of childbearing potential) • Serology: 
 - HIV antibody - hepatitis B surface antigen, hepatitis B core antibody, hepatitis C virus antibody - IgG antibodies against SARS-CoV-2 • Virology: nasopharyngeal or oropharyngeal swab for COVID-19 rRT-PCR test 
The results of each test must be entered into the CRF.
			

Abbreviations: COVID-19, Coronavirus Disease 2019; CRF, case report form; HIV, human immunodeficiency virus; Ig, immunoglobulin; pH, negative of the logarithm to base 10 of the activity of the (solvated) hydronium ion; rRT-PCR, real-time reverse transcription polymerase chain reaction; SARS-CoV-2, severe acute respiratory syndrome coronavirus 2.

^a The urine microscopy will be performed if the urinalysis parameter, such as leukocyte esterase, is out of normal range.

APPENDIX 5. CONTRACEPTION GUIDELINES AND DEFINITIONS OF “WOMEN OF CHILDBEARING POTENTIAL”, “NO CHILDBEARING POTENTIAL”

Contraception Guidelines

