6.5.3. Laboratory Values

Clinical laboratory values will be evaluated for each laboratory parameter as appropriate.

Descriptive summary statistics (n, mean, standard deviation, median, Q1, Q3, minimum, and maximum for continuous variables; n [%] for categorical variables) for laboratory parameters and their changes from baseline will be summarized by visit and dose level. Change from baseline will only be summarized for subjects with both baseline and postbaseline measurements.

Laboratory parameters that are graded in NCI-CTCAE v5.0 will be summarized by shifts from baseline CTCAE grades to maximum postbaseline grades. In the summary of laboratory parameters by CTCAE grade, parameters with CTCAE grading in both high and low directions will be summarized separately.

Subject data listings of each parameter will be provided. Abnormal values will be flagged and identified as those outside (above or below) the normal range.

BeiGene 12 May 2021

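### The x/2 rule for '< x' laboratory results in SAP 6.2.2 has no exception for tests whose scale does not start near zero; a urine specific gravity reported as '< 1.005' would be analysed as 0.5025

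*SAP*

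**What the plan says.** SAP 6.2.2 opens its list of conventions with "Unless otherwise specified, the following conventions will be applied to all analyses". Two of them deal with laboratory results that are not plain numbers. At the upper end: "For laboratory results collected as ≥ x, the value of the laboratory results will be set as x". At the lower end: "For laboratory results collected as < x, the value of the laboratory results will be set as x divided by 2". Neither SAP 6.2.2 nor SAP 6.5.3 exempts any test.

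Protocol Appendix 4 gives the urinalysis panel as "Specific gravity pH Glucose Protein Blood Ketones Bilirubin Urobilinogen Nitrite Leukocyte esterase". Protocol 10.3.3 counts urinalysis as part of the laboratory analysis: "Clinical laboratory (clinical chemistry, hematology, coagulation, and urinalysis) values will be evaluated for each laboratory parameter as appropriate".

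SAP 6.5.3 then says that "laboratory parameters and their changes from baseline will be summarized by visit and dose level", using "Descriptive summary statistics (n, mean, standard deviation, median, Q1, Q3, minimum, and maximum for continuous variables; n [%] for categorical variables". It does not say which tests are continuous and which are categorical.

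Protocol 8.2.3 sends the safety samples to a local laboratory. Neither document gives that laboratory's reporting format or limits.

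**The concern.** Setting `< x` to x/2 takes the midpoint of the interval from 0 to x. That makes sense for a concentration below an assay limit, where the true value may lie anywhere down to zero. It makes no sense for specific gravity, which is 1.000 for pure water, so that a result just under 1.005 can only be slightly lower than 1.005. Halving it gives a value that no urine sample can have.

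The groups are small: 6 active subjects per dose level (SAP 5) and a pooled placebo arm (SAP 6.2.1) of 4 subjects with two dose levels or 6 with three. One such value would dominate the mean, the SD and the mean change from baseline at that visit. Laboratory abnormalities are a secondary endpoint, and descriptive summaries are the only safety analysis planned. A table showing a mean specific gravity below that of water would mislead or, at best, prompt avoidable queries.

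**Working it through.** The plan states no figure on this point, so there is none to reproduce. The check applies the SAP rule as written and compares it with setting `< x` to x.

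**Inputs from the documents.** The x/2 rule (SAP 6.2.2); 6 active subjects per dose level (SAP 5); pooled placebo of 2 × 2 = 4 or 3 × 2 = 6 (SAP 5 and 6.2.1); 8 as the size of a whole cohort.

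**Assumed inputs.** Limits of `< 1.005` for specific gravity and `< 5.0` for urine pH, and all the uncensored values below.

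**Step 1, the substituted value.** 1.005 / 2 = 0.5025. For pH, 5.0 / 2 = 2.5.

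**Step 2, shift in a group mean from one such result.** Compared with using x, the shift is -(x/2)/n, whatever the other values are:
- n = 4: 0.5025 / 4 = 0.126
- n = 6: 0.5025 / 6 = 0.084
- n = 8: 0.5025 / 8 = 0.063

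The assumed limit hardly matters. At n = 6, a limit of 1.000 gives 0.500 / 6 = 0.083, and a limit of 1.010 gives 0.505 / 6 = 0.084.

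**Step 3, illustrative group of 6.** One `< 1.005` and five values of 1.010, 1.012, 1.015, 1.018 and 1.020. The censored subject's baseline is 1.012; the other five are unchanged from baseline.

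| | `< x` set to x | `< x` set to x/2 |
|---|---|---|
| Mean | 1.0133 | 0.9296 |
| SD | 0.0055 | 0.2093 |
| Median | 1.0135 | 1.0135 |
| Mean change | -0.0012 | -0.0849 |
| SD of change | 0.0029 | 0.208 |

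The SD grows about 38-fold (0.2093 / 0.0055). The censored subject's own change is 0.5025 - 1.012 = -0.5095. Divided by 6, this gives the group mean change of -0.0849, a shift of about -0.08 from the value under x.

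**Step 4, more than one such result.** Replacing the lowest values in turn, two of six give a mean of 0.845 and leave the median at 1.0135. Three of six give a mean of 0.760, and the median falls to 0.759.

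**Step 5, a censored baseline.** Baseline is the last value before dosing (SAP 6.2.1). If that value is `< 1.005` and later results are numeric, the sign reverses: the group mean change is too high by 0.5025 / 6 = 0.084 at every later visit at which urinalysis is done. If baseline and follow-up are both `< 1.005`, the change is zero.

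**Step 6, urine pH.** One `< 5.0` with 5.5, 6, 6, 6.5 and 7: the mean is 6.00 using x and 5.58 using x/2 (shift 2.5 / 6 = 0.42). The SD goes from 0.71 to 1.59, and the median stays at 6.0.

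**The case against.** The strongest reply is that the trigger may never occur. The rule acts only on results collected with a `<` sign, and nothing in the documents shows that the local laboratory reports specific gravity or pH that way. SAP 6.5.3 also leaves room to treat these tests as categorical, in which case no halved value enters a mean. Both points stand and make the concern conditional. They do not remove it, because the SAP neither classifies the tests nor exempts them.

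Several stronger readings are tempting, and the documents do not support them:

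- A reader might infer that any low specific gravity, or any dilute urine, is halved. It is not: a numeric 1.005 stays 1.005.
- A reader might take a change of about -0.5 as the group result. It is one subject's change; the group mean change is about -0.08.
- A reader might call both urine values impossible. That fits 0.5025. A pH of 2.5 is a valid pH and only implausible for urine.
- A reader might extend the point to INR. It is a ratio, the documents do not place its scale away from zero or give a reporting limit, and no calculation here covers it.
- A reader might see the different handling of `≥ x` and `< x` as a contradiction. A result `≥ x` can equal x and a result `< x` cannot, so different substitutions are defensible in themselves.
- A reader might infer that abnormality counts or the pausing rules are affected. No changed flag or CTCAE grade shift has been shown, and the pausing criteria in protocol 3.3 rest on adverse events, not on laboratory means.

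It is also fair that the SAP requires the median and the minimum. The median would be unmoved by one or two such results in six, and a minimum of 0.50 would be conspicuous to a careful reader.

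**Conclusion.** The point holds as a conditional drafting gap, centred on specific gravity. As written, the SAP would analyse `< 1.005` as 0.5025, and one such result in a group of 6 would put the by-visit mean about 0.084 too low relative to using x (0.126 at n = 4, 0.063 at n = 8). The size of that shift does not depend on the illustrative data; the SD figures do. The conclusion rests on two assumptions that the documents neither confirm nor exclude: that a result is collected as `< x`, and that the test is summarised as continuous. If either fails, the effect is nil. The consequence is confined to a descriptive summary of secondary safety data. The priority is low, and the reason to act is that the correction is so cheap.

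**What to change.** In SAP 6.2.2, limit the x/2 substitution to analytes reported below a quantification limit on a scale that starts at zero. For urine specific gravity and urine pH, state one of two alternatives before the tables are programmed: set `< x` to x, or summarise the test by category, which SAP 6.5.3 already allows and which needs no substitution.

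The cost is one SAP sentence and a two-item exception list in the programming specification. Using x carries a slight upward bias, because the true value lies a little below x. If no `<` result is ever reported for these tests, the change alters nothing.

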6.2.3. Handling of Missing Data

Missing data will not be imputed unless otherwise specified elsewhere in this SAP. Missing dates or partially missing dates will be imputed conservatively for adverse events and prior/concomitant medications/procedures. Specific rules for the handling of missing or partially missing dates for adverse events and prior/concomitant medications/procedures are provided in Appendix A.

By-visit endpoints will be analyzed using observed data unless otherwise specified. For observed data analyses, missing data will not be imputed, and only the observed records will be included.

6.2.4. Multiplicity Adjustment

No multiplicity adjustments will be made in this study.

6.2.5. Data Integrity

Before pre-specified final analysis begins, the integrity of the data should be reviewed to assure fit-for-purpose. The data set for analysis should be an accurate and complete representation of the subjects' relevant outcomes from the clinical database. All data should be complete and reviewed up to a pre-specified cutoff date as specified in the Data Extract and Snapshot Plan. Consistency checks and appropriate source data verification should be completed as specified in the Site Monitoring Plan.

6.3. Subject Characteristics

6.3.1. Subject Disposition

The number (percentage) of subjects randomized, treated, discontinued from the study drug and/or study will be counted by dose level. The primary reason for subjects randomized but not treated and study drug and/or study discontinuation will be summarized according to the categories in the eCRF. A listing of subject disposition will be provided.

6.3.2. Protocol Deviations

Important protocol deviation criteria will be established, and subjects with important protocol deviations will be identified and documented.

Important protocol deviations will be summarized and listed by category for all subjects in the Safety Analysis Set. Deviation categories are not mutually exclusive. Multiple deviations within the same category are counted once per subject.

BeiGene 12 May 2021

6.3.3. Demographic and Other Baseline Characteristics

Demographics and other baseline characteristics will be summarized by dose level using descriptive statistics in the Safety Analysis Set. Summary statistics will be presented for continuous variables, and the number (percentage) of subjects in each category will be presented for categorical variables. Continuous variables include but are not limited to age, height, weight, and body mass index (BMI). Categorical variables include but are not limited to sex, race, and ethnicity. A listing of demographics and other baseline characteristics will be provided.

6.3.4. Prior and Concomitant Medications

Prior medications will be defined as medications that started and stopped before the dose of study drug. Concomitant medications will be defined as medications that (1) started before the dose of study drug and were continuing at the time of the dose of study drug, or (2) started on or after the date of the dose of study drug up to 30 days after the dose of study drug.

Prior and concomitant medications will be coded using the version of World Health Organization Drug Dictionary (WHO DD) drug codes currently in effect at BeiGene at the time of database lock. They will be further coded to the appropriate Anatomical Therapeutic Chemical (ATC) code indicating therapeutic classification.

The number (percentage) of subjects reporting prior and concomitant medications will be summarized by ATC medication class and WHO DD preferred name in the Safety Analysis Set. A listing of prior and concomitant medications will be provided.

6.3.5. Medical History

Medical History will be coded using Medical Dictionary for Regulatory Activities (MedDRA) version currently in effect at BeiGene at the time of database lock. The number (percentage) of subjects reporting a history of any medical condition, as recorded on the CRF, will be summarized by system organ class (SOC) and preferred term (PT) in the Safety Analysis Set. A listing of medical history will be provided.

6.4. Efficacy Analysis

There is no efficacy analysis planned for this study.

6.5. Safety Analyses

All safety analyses will be performed based on the Safety Analysis Set. Descriptive statistics will be used to analyze all safety data.

6.5.1. Extent of Exposure

The extent of study drug exposure will be summarized descriptively for the single dose administered by dose level. The number (percentage) of subjects with dose interruption and infusion rate decreased will be summarized with the respective reasons by dose level.

Subject data listings will be provided for all dosing records.

BeiGene 12 May 2021

6.5.2. Adverse Events

The AE verbatim descriptions (investigator terms from the eCRF) will be classified into standardized medical terminology using MedDRA. Adverse events will be coded to the MedDRA lowest level term closest to the verbatim term, along with the linked MedDRA PT and primary SOC.

A TEAE is defined as an AE that had an onset date or a worsening in severity from baseline on or after the administration of study drug and up to 30 days after the dose of study drug. Summary tables will generally focus on those AEs that were treatment-emergent. All AEs, treatment-emergent or otherwise, will be presented in subject data listings.

If any of the following TEAEs occurs, the administration of the study drug and the enrollment of new subjects will pause for the dose level:

- One or more ≥ Grade 4 TEAEs or treatment-emergent SAEs related to study drug as assessed by the investigator in any subject or
- Grade 3 TEAEs related to study drug as assessed by the investigator in 2 or more subjects at the same dose level.

An AE overview table, including the number of subjects with TEAEs, TEAEs with grade 3, TEAEs with grade 4 or higher, treatment-emergent SAEs, TEAEs that led to death, TEAEs that led to treatment discontinuation, TEAEs that led to treatment modification for study drug, and treatment-related TEAEs, will be provided by dose level. Treatment-related AEs include those events considered by the investigator to be related to study drug or with a missing assessment of the causal relationship.

The incidence of TEAEs will be reported as the number (percentage) of subjects with TEAEs by SOC, PT and the worst grade. A subject will be counted only once by the highest severity grade according to NCI-CTCAE version 5.0 within a SOC and PT, even if the subject experienced more than one TEAE within a specific SOC and PT. The number (percentage) of subjects with treatment-emergent SAEs will be summarized by SOC and PT.

6.5.3. Laboratory Values

Clinical laboratory values will be evaluated for each laboratory parameter as appropriate.

Descriptive summary statistics (n, mean, standard deviation, median, Q1, Q3, minimum, and maximum for continuous variables; n [%] for categorical variables) for laboratory parameters and their changes from baseline will be summarized by visit and dose level. Change from baseline will only be summarized for subjects with both baseline and postbaseline measurements.

Laboratory parameters that are graded in NCI-CTCAE v5.0 will be summarized by shifts from baseline CTCAE grades to maximum postbaseline grades. In the summary of laboratory parameters by CTCAE grade, parameters with CTCAE grading in both high and low directions will be summarized separately.

Subject data listings of each parameter will be provided. Abnormal values will be flagged and identified as those outside (above or below) the normal range.

BeiGene 12 May 2021

6.5.4. Vital Signs

Descriptive statistics for vital sign parameters (systolic and diastolic blood pressure, pulse rate, respiratory rate, and body temperature) and changes from baseline will be summarized by visit and dose level.

Subject data listings of each parameter will be provided. Abnormal values will be flagged and identified as those outside (above or below) the normal range. Reference (normal) ranges for vital signs parameters are defined as following:

• Respiratory rate: 10-22 bpm

• Temperature: 35.5-37.5 °C

• Systolic blood pressure: 90-140 mmHg

• Diastolic blood pressure: 40-90 mmHg

• Pulse rate: 60-100 bpm

6.5.5. Electrocardiograms (ECG)

Descriptive statistics for ECG parameters (heart rate and QTcF interval) and changes from baseline will be summarized by visit and dose level.

Subject data listings of each parameter will be provided. Abnormal values will be flagged and identified as those outside (above or below) the normal range. Reference (normal) ranges for ECG parameters are defined as following:

Heart rate: 60-100 bpmQTcF interval: ≤450 msec

6.6. Pharmacokinetic Analyses

The following analysis plan provides the framework for the summarization of the PK data. The objective is to assess BGB-DXP593 PK and characterize PK parameters following a single intravenous dose. The PK analyses will include only subjects randomized to receive BGB-DXP593 and with enough data to enable estimation of key parameters. Additional PK analyses (such as modeling and simulation using nonlinear mixed effects modelling) may be conducted if deemed necessary and will be described in a separate analysis plan.

6.6.1. Calculation of Serum Pharmacokinetic Parameters

Actual dose and blood draw times will be used to calculate the PK parameters. Parameters will be listed individually and summarized by dose level using descriptive statistics.

The following plasma PK parameters will be calculated for BGB-DXP593, as appropriate for the data collected. Other PK parameters may be calculated if supported by the data.

Calculation and presentation of PK parameters will be based on the Work Instruction: Best Practice Guidance: Non-Compartmental Pharmacokinetic Data Analysis for Clinical Studies. Version 1.0, Document Number VV-QDOC-13140.

Parameter (Units)	Definition	Method of Determination
AUC ₀₋₂₉ (μg·day/mL)	Area under the serum concentration versus time curve from Day 1 to Day 29	Calculated using the linear up/log down variant of the trapezoidal rule
AUC _{inf} (μg·day/mL)	AUC from zero to infinite time with extrapolation of the terminal phase	Calculated using the linear up/log down variant of the trapezoidal rule
AUC ₀₋₈ (μg·day/mL)	Area under the serum concentration versus time curve from Day 1 to Day 8	Calculated using the linear up/log down variant of the trapezoidal rule
AUC ₀₋₁₅ (μg·day/mL)	Area under the serum concentration versus time curve from Day 1 to Day 15	Calculated using the linear up/log down variant of the trapezoidal rule
AUC _{last} (μg·day/mL)	AUC from time zero to time of last quantifiable concentration	Calculated using the linear up/log down variant of the trapezoidal rule
C _{max} (µg/mL)	Maximum observed drug concentration during a dosing interval	Reported value
t _{max} (h)	Time to reach C _{max}	Actual elapsed time for reported C _{max}
$t_{1/2}$ (days)	half-life	$ln(2)/\lambda_z$, where λ_z is the first-order rate constant of drug associated with the terminal portion of the curve
CL (L/h)	clearance	Calculated as Dose/AUC _{inf}
$V_z(L)$	volume of distribution during the terminal phase	Calculated as CL/λ_z , where λ_z is the first-order rate constant of drug associated with the terminal portion of the curve

